13.0 PHOTOGRAPHY

Standardized photographs will be taken of the treatment area. The subject will be asked to remove jewelry, make-up, and lotions prior to each photo session. Photographs will be taken with an appropriate high-resolution digital camera. Camera settings (lighting, distance, background, polarization, etc.) will be reproduced at each visit, so that photographs are suitable for comparison. Photographs will be taken of the treatment area for study purposes. If the subject does not wish to have their photographs taken, they cannot be in the study.

14.0 ADVERSE REACTIONS DEFINITIONS AND REPORTING REQUIREMENTS

All adverse events that occur, starting from the time of the first treatment, will be recorded in the source documents and Case Report Forms (CRF).

Adverse Events (AE) occurring will be captured and followed until the condition resolves, stabilizes, is otherwise explained, or the subject is lost to follow-up. Subjects will be instructed that they may contact the Investigator at any time throughout the course of the study.

The Investigator and/or designated study staff will review each event and assess its relationship to the study device (not related, unlikely, possible, probable, and highly probable). The following definitions will be used for rating relationship to the TempSure® treatments:

- Not related – The event is clearly related to other factors such as the subject’s clinical state, therapeutic interventions, or concomitant medications administered to the subject.
- Unlikely – The event was most likely produced by other factors such as the subject’s clinical state, therapeutic interventions, or a concomitant medication administered to the subject; and does not follow a known response pattern to the investigational product.
- Possible – The event follows a reasonable temporal sequence from the time of investigational product administration; **and/or** follows a known response pattern to the study sampling sessions; **but** could have been produced by other factors such as the subject’s clinical state, therapeutic interventions, or concomitant medications administered to the subject.

- Probable – The event follows a reasonable temporal sequence from the time of investigational product administration; **and** follows a known response pattern to the investigational product; **and** cannot be reasonably explained by other factors such as the subject’s clinical state, therapeutic interventions, or concomitant medications administered to the subject.
- Highly Probable – The event follows a reasonable temporal sequence from the time of investigational product administration; **and** follows a known response pattern to the investigational product; **and** cannot be reasonably explained by other factors such as the subject’s clinical state, therapeutic interventions, or concomitant medications administered to the subject; **and** either occurs immediately following investigational product administration, **or** improves on stopping the investigational product, **or** reappears on repeat exposure, **or** there is a positive reaction at the application site.

Each adverse event reported will be graded on a 3-point severity. Using the following definitions for rating severity will be used:

- Mild – easily tolerated, causing minimal discomfort, and not interfering with normal everyday activities.
- Moderate – sufficiently discomforting and may interfere with normal everyday activities.
- Severe – incapacitating and/or preventing normal everyday activities.

A Serious Adverse Event (SAE) is any adverse device experience that results in any of the following outcomes: death, a life-threatening adverse device experience, in-patient hospitalization or prolongation of hospitalization, a persistent or significant disability/incapacity, or a congenital anomaly/birth defect. Important medical events that may or may not result in death, be life-threatening, or require hospitalization may be considered a serious adverse device experience when, based upon appropriate medical judgment, they may jeopardize the subject or subject may require medical or surgical intervention to prevent one of the outcomes listed in this definition

If any of the above adverse events are serious as defined by the FDA Code of Federal Regulations (CFR), Title 21, special procedures will be followed. All serious adverse events will be reported within 24 hours of acknowledgment to the Sponsor whether or not the serious events are deemed sampling session-related. All serious event reporting will adhere to 21 CFR part 812 and the IRB will be notified accordingly.

The SAE information will be entered into the database and a desk copy of the complete SAE report will be submitted to the study file.

Adverse events, whether serious or non-serious, will be followed until the condition is resolved, stabilized, otherwise explained or the subject is lost to follow-up. Adverse events will be captured throughout the study and where appropriate, medical tests and examinations will be performed to document the resolution of event(s). Outcomes may be classified as resolved, improved, unchanged, worse, fatal, unknown or lost to follow-up. Following the resolution of any study-associated adverse events there will be no further adverse event reports for that subject.

Reporting Adverse Events:

Report	Submit To	Description/Constraints
Adverse Events, Unanticipated Adverse Device Effect	IRB and Sponsor	If an unforeseen complication is determined to be an unanticipated adverse device effect, the investigator’s report must be submitted within 10 working days after the investigator first learns of the effect.
Serious Adverse Events	IRB and Sponsor	The sponsor must be notified within 24 hours of serious adverse events. The IRB must be notified within 1 working day of serious adverse events as defined by FDA guidelines.

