- The subject is allergic to corn, such as the corn derivative ingredient in Parker Aquasonic Gel.
- If the subject has an unhealthy expectation of the results – this is not plastic surgery and all subject should be fully informed of the treatment’s expected results.
- The subject has severe laxity or sagging that causes redundant folds of tissue or hanging skin in the area to be treated – this treatment will be ineffective.
- The subject has used Accutane (Isotretinoin) six to twelve months prior to treatment, as this can thin the skin and make it brittle.
- Studies of the use of the RF generator on subjects that have any of the following conditions is unknown:
 - Autoimmune Disease
 - Diabetic
 - Herpes Simplex
- Use caution when treating areas that have scars, tattoos, permanent makeup, and permanent brows.

Exclusion Criteria for Icon Treatments Only:

- The subject is using systemic steroids (e.g. prednisone, dexamethasone) prior to or during the course of treatment.
- The subject has a medical condition or is receiving treatment that significantly compromise healing response.
- The subject has a history of light-induced seizures.
- The subject has a history of skin photosensitivity disorders.
- The subject has a history of hypertrophic scars or keloid formation.
- The subject has a history of radiation therapy in area to be treated.

Additional Cautionary Criteria for Icon Treatments Only:

- The subject is not allergic to medications, latex or other substances that may be used during treatment course.
- The subject’s skin type is appropriate for the handpiece to be used.
- The subject is taking photosensitizing medication. Perform test spots 24 hours up to one week before considering treatment.

- The subject is currently taking blood thinning medications or anti-coagulants. The subject should discontinue the use of these medications if determined to be safe to do so by their prescribing physician. With the prescribing physician's approval, the subject should stop taking the medication at least 2 weeks prior to and throughout the treatment course.
- The subject has a condition or is taking medications that alters the ability of the blood to coagulate.

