2.7 Treatment Procedures

- Prior to treatment 1 only, subjects will be asked to complete a Pre-Treatment 1 Questionnaire.
- The defined study area will be identified and may be marked with a surgical marker.
- Procedures for the TempSure treatment:
 - A neutral pad will be placed on the back in an area determined by the Investigator to maintain standard energy settings and to require less power from the device during the treatment.
 - The subject may be required to wear eye shields at the discretion of the Investigator.
 - Gel will be applied to the treatment area.
 - The handpiece will be placed in contact with the skin.
 - The entire defined treatment area will then be treated by delivering energy to the skin.
 - Temperature will be continuously monitored and recorded during treatment.
- Procedures for the Icon treatment:
 - All operators and subjects will wear appropriate protective eyeglasses during the pulse-light treatments.
 - The Skintel Melanin Reader may be used for objective measurement of the melanin content of skin. The Skintel Reader may provide guidance to help select test spot settings.
 - Test spots will be performed prior to treatment in an area in or close to the treatment area in order to determine safe parameters for treatment.
 - The handpiece will be placed in contact with the skin.
 - The entire defined treatment area will then be treated by delivering adjacent pulses with minimal overlap of 20% or less.

- An air-cooling system may be used during treatment. The air-cooling system allows for the continuous flow of cold air on the treatment area to ease the sensation from the pulse.
- Parameters may be adjusted throughout the treatment to increase subject comfort.
- Subjects will be asked to report the general level of treatment discomfort/pain on a scale of 0 (none) to 10 (maximum intolerable pain).
- Photographs may be taken during treatment.
- The additional treatments will follow the same procedure.
- Subjects will receive up to 4 treatments on the face. Subjects in group B may be asked to return for an optional 5th treatment with the Icon device (and/or TempSure device) at the discretion of the Investigator.

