2.12 Schedule of Visits and Procedures

	Visit #1*	Visit #2 - 5	Treatment Visit*** (Optional)	Call (Optional)	Visit #6	Visit #7
Procedure	Screening and Pretreatment Procedures	Treatment Visits 1-4 (1 - 2 weeks apart)	Treatment Visit #5 (2 - 3 weeks post last treatment)	Phone Call 1 Week Post Each Tx (1-7 Days)	Follow Up 4 Weeks Post Last Tx (+/- 1 Week)	Follow Up 12 Weeks Post Last Tx (+/- 1 Week)
Medical History	X					
Pregnancy Verification**	X	X	X			
Informed Consent	X					
Photographs	X	X	X		X	X
FWSS	X				X	X
Subject Pre-Treatment 1 Questionnaire		X				
Treatment		X	X			
Treatment Discomfort/ Pain Evaluation		X	X			
Subject Post Treatment 1 Questionnaire		X				
PGAIS					X	X
SGAIS					X	X
Subject Follow Up Questionnaire					X	X
Adverse Events Assessment	X	X	X	X	X	X

*Screening and Pretreatment Procedures may occur at the same time as the first Treatment Visit.

**Pregnancy verification required before each treatment only for women of childbearing potential.

***Group B only

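### Section 14.0 starts adverse event recording at the first treatment, which contradicts 2.12 and its own later text; a reaction to an early Icon test spot could go unrecorded

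*Combined protocol and SAP*

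**What the plan says.** The plan gives more than one start for adverse event recording.

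- **14.0, opening sentence:** "All adverse events that occur, starting from the time of the first treatment, will be recorded in the source documents" (and the case report forms).
- **14.0, later text:** "Adverse events will be captured throughout the study". Section 2.15.6 likewise describes collection over the course of the study.
- **2.12, schedule:** the row "Adverse Events Assessment" is marked in every column, including Visit 1 (screening and pretreatment), which is separate from the treatment visits. A footnote adds: "Screening and Pretreatment Procedures may occur at the same time as the first Treatment Visit". Visit 1 may therefore also fall on an earlier day.
- **2.5:** a subject counts as enrolled on signing consent.

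On Icon test spots:

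- **2.7, under the Icon procedures:** "Test spots will be performed prior to treatment in an area in or close to the treatment area in order to determine safe parameters".
- **2.3, Icon cautionary criteria, for subjects on photosensitising medication:** "Perform test spots 24 hours up to one week before considering treatment".

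On analysis, 2.15.3 limits the safety set to randomised patients who have had at least one treatment and have some safety data.

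**The concern.** A test spot is a study-device exposure on or near the face, made to find out which settings are safe. That it delivers energy is an inference from this purpose and from the mention of test spot settings in 2.7; the protocol does not say so in those words. Section 2.14 lists burns, pigment change and scarring among the possible Icon effects. If recording starts at the first treatment, a reaction to an earlier test spot falls in a period for which the governing section requires no record.

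The possible loss is not random. The subjects for whom the protocol asks for a test spot on an earlier day are those it singles out for caution because of photosensitising medication. A reaction to the test spot may also be the reason a subject is never treated, which removes that subject from the safety set. Section 2.15.1 makes an acceptable side effect profile one of the conditions for success on the additional assessments, so any such omission would work in the device's favour.

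**Working it through.** No stated figure is in question. The check sets the sections side by side and works out on which days a test spot can fall. Take the day of the first study treatment as day 0.

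**1. When does recording open?**
- 14.0, opening sentence: day 0.
- 2.12: Visit 1, which is before day 0 unless screening and first treatment share a day.
- 14.0, later text, and 2.15.6: throughout the study, which under 2.5 a subject enters at consent.

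Whenever Visit 1 is on an earlier day, the schedule asks for an assessment whose findings the opening sentence of 14.0 does not require anyone to record. This conflict exists with or without Icon.

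**2. When can a test spot fall?** Section 2.3 gives an interval of 24 hours to one week, that is 1 to 7 days, for subjects on photosensitising medication. Section 2.12 puts treatments 1 to 2 weeks apart. Section 2.1 gives Group B two TempSure-only and two combined sessions, in no stated order.
- *Icon used at session 1:* test spot between day 0 − 7 = −7 and day 0 − 1 = −1. This is before the 14.0 start, by at most 7 days.
- *Icon first used at session 2:* session 2 is between day 7 and day 14, so the test spot is between day 7 − 7 = 0 and day 14 − 1 = 13. This is on or after the day of the first treatment, so inside the 14.0 period except possibly for a few hours on day 0.
- *Icon first used later:* the test spot falls later still and is inside the period.
- *Other Group B subjects:* 2.7 gives no interval. The test spot may be on the treatment day, where a reaction still present would be seen when adverse events are documented after treatment (2.8).

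Under the protocol's own timing, then, the multi-day gap needs three conditions together: Group B, photosensitising medication, and Icon at the first session.

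**3. Would another contact pick the event up?** The schedule has no test-spot visit. The optional one-week call follows treatments, not test spots. An event still present at the first treatment visit would probably be noticed. One that has resolved by then, or that occurs in a subject who is not treated, might not be.

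**4. Would the event be analysed?** Under 2.15.3 the safety set needs at least one treatment. No section defines a test spot as a treatment. A subject exposed only to a test spot is therefore outside the set even if the event was written down.

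**5. How many subjects?** The documents do not give the size of Group B, the number on photosensitising medication or the session order. The only bound is the total enrolment of up to 50.

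**The case against.** Five arguments limit the point.

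- **The plan does not consistently exclude early events.** A reader might infer from the opening of 14.0 that events are recorded only from the first treatment. The later sentence in 14.0, 2.15.6 and the Visit 1 assessment say otherwise. This stands: the defect is a contradiction that allows events to be missed, not a uniform rule that drops them.
- **Test spots may count as part of treatment.** They are listed as a step under the Icon procedures in 2.7, and a site could read them that way. This stands in part. The same step is described as preceding treatment, and an interval of up to a week is hard to fit into one treatment visit. With three centres and no definition, sites could record differently.
- **The group is narrow.** This stands. If a TempSure-only session always comes first, the test-spot gap all but disappears, although the conflict over Visit 1 remains.
- **Serious events have their own route.** 14.0 requires every serious event to reach the sponsor within 24 hours and unanticipated device effects to be reported within 10 working days, and neither rule restates a first-treatment start. This stands, so the gap concerns mainly non-serious reactions.
- **The safety set is faulty for another reason.** Section 2.15.3 requires randomisation, but 2.1 says there is none, so read literally nobody qualifies. That is true and needs its own correction. Removing the word would still leave the requirement of one treatment.

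**Conclusion.** The sections conflict on when adverse event recording starts and should be reconciled. The practical consequence is limited: a reaction to an Icon test spot made before any study treatment could go unrecorded under 14.0, and it would be outside the safety set if the subject is never treated. The exposed period is 1 to 7 days for Group B subjects on photosensitising medication whose first session includes Icon. For other Group B subjects no interval is stated.

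A reader might go further and infer that the Icon adverse event rate is understated. The documents do not show that. The number affected is unknown and may be small or zero. Sites that follow 2.12 and the later text of 14.0 would record these events, and 2.15.6 plans descriptive summaries with no comparison. Understatement is possible, not certain.

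The conclusion rests on two assumptions: that a test spot is a device exposure capable of causing a reaction, and that it is not counted as a treatment. It is still worth acting on, because a stated rule can omit device-related safety events and the correction is cheap.

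**What to change.** - **14.0:** replace the opening start point so that recording begins no later than the first device exposure, test spots included. Starting at consent would also serve and would match the Visit 1 assessment in 2.12. First device exposure is enough for the test-spot gap, but the Visit 1 assessment would then need a note on how earlier findings are handled.
- **14.0 or 2.7:** state whether a test spot counts as a treatment for adverse event recording, so that all centres read it alike.
- **2.15.3:** add that events in subjects exposed only to a test spot will be listed, separately from the safety set summaries.

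The cost is about two sentences, plus the clarification on test spots. No visit or procedure is added, since the Visit 1 assessment is already scheduled. The downside is a few more unrelated events on record, somewhat more if recording starts at consent. The timing of test spots need not change for this purpose.

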2.14 Adverse Event Recording

All data captured must be supported by the Investigator’s timely assessment and documentation of the adverse event in the case report forms or source documents. All documented adverse events will be reviewed by the Sponsor or designee to determine whether the adverse event meets regulatory reporting requirements and to ensure timely adverse event reporting to meet local and global regulatory requirements. All adverse events must be followed until their resolution.

Adverse Events Pertaining to the TempSure Device:

Mild discomfort during treatment may be experienced by the subject. Typically, the discomfort is temporary and localized within the treatment area. Mild edema (swelling) and erythema (redness) may occur. Initial studies indicate that these side effects typically resolve within 2 to 24 hours.

Other anticipated side effects may include; pain, skin burns, bleeding, scarring, crusting, bruising, infection, itching, prolonged edema (swelling) and erythema (redness), hardness, and nodules. Loss of hair pigment may also occur within and adjacent to the treatment area.

Adverse Events Pertaining to the Icon Device:

Adverse effects can include discomfort/pain, redness, swelling, pinpoint bleeding, skin peeling, itching, scabbing, crusting, purpura, and bruising, which are usually transient and resolve without intervention.

Possible adverse effects include pustules (such as ingrown hairs), skin burns, hypopigmentation, hyperpigmentation, removal or lightening of freckles, scarring, infection and allergic reaction (such as a rash). There is also risk of incidental hair reduction or removal in the treated areas.

People of Middle Eastern and Mediterranean descent and those who have an ill-defined hair line with no obvious transition of the hairline to the face are at a high risk for hair stimulation (paradoxical hair growth).

Adverse Events Pertaining to Gel:

The gel is a water-based gel that may be placed on the skin during the TempSure® treatment. No known adverse events are documented. However, an allergic reaction is always possible when placing a topical gel onto the skin. Allergic reaction may include a mild reaction such as skin redness, irritation, or hives.

Adverse Events Pertaining to Neutral Pad:

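### As worded, section 14.0 ends adverse event reports by subject once events resolve, which conflicts with the plan's own recording or expedited-reporting rules

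*Combined protocol and SAP*

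**What the plan says.** Section 14.0 opens with a broad recording rule: "All adverse events that occur, starting from the time of the first treatment, will be recorded" in the source documents and case report forms. Each event is then "followed until the condition resolves, stabilizes, is otherwise explained, or the subject is lost to follow-up".

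The paragraph just above the reporting table repeats those follow-up end points and states that "Adverse events will be captured throughout the study". It closes with: "Following the resolution of any study-associated adverse events there will be no further adverse event reports for that subject".

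The same section has two expedited rules. On serious events: "All serious adverse events will be reported within 24 hours of acknowledgment to the Sponsor", whether or not they are judged related to a session. The table adds IRB notification within 1 working day. On unanticipated effects: "If an unforeseen complication is determined to be an unanticipated adverse device effect", the investigator's report is due within 10 working days of first learning of it.

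Elsewhere, events are documented after treatment (section 2.8) and at every follow-up visit (section 2.9). Adverse event assessment is marked in every column of the visit schedule (section 2.12), and the safety analysis relies on collection over the whole study (section 2.15.6).

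**The concern.** The closing sentence is triggered by resolution of an event, but what it ends is reporting for the subject. It makes no exception for new, serious or unanticipated events, and it is not confined to the period after the last visit. Treatment is repeated, and section 2.14 expects the common TempSure reactions to clear within a day, so the trigger could be met between the first and second sessions.

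Adverse event collection is a safety objective (section 1.2), and an acceptable side effect profile is one of the success conditions (section 2.15.1). If a site took the sentence as a recording rule, event types that first appear at later sessions or follow-up visits could be missing from the percentages in section 2.15.6. If a site took it as a rule about submissions, those summaries would be intact. The site would then have two answers on whether a later serious event or unanticipated device effect must be sent on.

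**Working it through.** The plan states no figure to reproduce. The check sets the passages side by side under each meaning of a report, then counts visits.

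**1. Report means recording.** Section 14.0 uses the word this way when it says "Each adverse event reported will be graded on a 3-point severity", since grading applies to every recorded event. On this meaning the closing sentence contradicts the capture rule in its own paragraph, the opening rule of section 14.0, and sections 2.8, 2.9, 2.12 and 2.15.6.

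**2. Report means formal submission.** Section 2.14 supports this meaning, because it separates documenting an event from deciding whether to submit it: "All documented adverse events will be reviewed by the Sponsor or designee to determine whether the adverse event meets regulatory reporting requirements". Recording then continues and the conflicts in step 1 fall away. The sentence now contradicts the serious-event and unanticipated-effect rules, which are themselves submission rules. Neither exempts a subject whose earlier event has resolved.

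**3. Does the word any help?** If it is read as all, the condition is still met whenever every study-associated event so far has resolved, which can happen between sessions.

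**4. How much of the schedule would fall after the cut-off (step 1 meaning only).** Inputs:
- treatments 1 to 2 weeks apart (section 2.12)
- final visit 12 weeks ± 1 week after the last treatment (section 2.12)
- optional fifth treatment 2 to 3 weeks after the fourth, Group B only (section 2.12)
- usual TempSure redness or swelling lasting 2 to 24 hours (section 2.14).

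Take a TempSure reaction to treatment 1 that resolves before treatment 2. With k treatments, the required assessments from first treatment onward number k + 2 (k treatment visits and two follow-up visits). Those after treatment 1 number (k − 1) + 2 = k + 1.

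| k | Assessments after cut-off |
|---|---|
| 1 | 2 of 3 |
| 2 | 3 of 4 |
| 3 | 4 of 5 |
| 4 | 5 of 6 |
| 5 (Group B option) | 6 of 7 |

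Fewer than four treatments is a Group A case under section 2.1, which assigns Group B two plus two. Optional phone calls are not counted.

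Time from treatment 2 to the final visit, k = 4:
- shortest: 2 × 1 + 11 = 13 weeks
- longest: 2 × 2 + 13 = 17 weeks.

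Measured from treatment 1 it is 3 × 1 + 11 = 14 to 3 × 2 + 13 = 19 weeks. With the fifth treatment, treatment 2 to the final visit is 2 × 1 + 2 + 11 = 15 to 2 × 2 + 3 + 13 = 20 weeks. Section 2.9 also lets a COVID-affected subject have the final visit up to 1 year after the last treatment, so these are not upper limits for everyone.

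The counts are not applied to Icon reactions. Section 2.8 gives 7 to 21 days for treated pigmented lesions to start flaking off, which can run past the next session.

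**The case against.** The best defence is context. The paragraph is about follow-up: events are followed to an end point, resolution is documented, outcomes are classified, and then the process is closed. In that setting the sentence can be read as closing the resolved event, or as a close-out once all study-associated events have resolved and the study period is over. On either reading, capture during the study is untouched. Section 14.0 also commits serious-event reporting to 21 CFR part 812, section 17.0 requires compliance with FDA regulations, and the table with fixed deadlines sits directly below. A site would hardly treat one loose sentence as overriding all of that. Sponsor training, monitoring and case report form review (section 5.0) add further protection.

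Much of this stands. The benign intent is the likelier one, and these safeguards make a missed report less likely. But the sentence contains neither limit, and event-level follow-up is already closed by the first sentence of the same paragraph. A close-out reading would still leave the 10-working-day clock unaddressed, since it starts when the investigator learns of the effect and has no end date. Sponsor review under section 2.14 covers documented events only, so it cannot recover one that was never recorded.

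A reader might go further and infer that later events will in fact go unrecorded, or that the safety percentages are understated by a known amount. The documents do not support that. They give no adverse event rates, and the visit counts show exposure to the ambiguity, not events lost.

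**Conclusion.** The conflict is real on the text and should be corrected. It is a drafting defect in a safety rule; nothing in the documents suggests an intention to stop collecting events. Under the literal recording meaning, 5 of 6 required assessments for a four-treatment subject would follow the cut-off, over 13 to 17 weeks by schedule. This assumes that a TempSure reaction to treatment 1 resolves before treatment 2 and that the site follows the sentence as written. Under the submission meaning the safety summaries are unaffected, and the problem is contradictory instructions on expedited reporting.

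A reader might also infer that the study's success decision is compromised. That does not follow. The photographic primary endpoint and the pain scores do not depend on this sentence. The share of subjects with any event is also safe, because the cut-off applies only after a subject already has one. No test or numeric threshold uses event counts: section 2.15.6 rules out statistical comparisons, and section 2.15.1 leaves acceptability to the physician's judgement.

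**What to change.** Reconcile the passages by limiting the closing sentence of section 14.0 to the event. For example:

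*Once an adverse event has resolved, stabilized or been otherwise explained, or the subject is lost to follow-up, no further follow-up reports are required for that event. New adverse events continue to be recorded through the subject's last study visit, including any final visit after withdrawal or removal. This does not limit the serious adverse event and unanticipated adverse device effect reporting requirements in this section.*

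The last sentence is needed because the 24-hour and 10-working-day rules carry no end date, and a stop at the last visit or at withdrawal would add one. The mention of final visits is needed because sections 11.0 and 12.0 ask subjects who are removed for pregnancy or who withdraw to attend one. Section 12.0 also says that no data are collected after withdrawal, which sits badly with its own final visit and should be reconciled in the same edit.

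The cost is small: a replacement for one sentence in section 14.0 and a matching edit to section 12.0. Section 21.0 requires written IRB approval for any revision, so the change can travel with the next amendment. It adds no visit or procedure, because adverse event assessment is already marked throughout the schedule.
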